2 OBJECTIVES

Primary objective:

- *Determine whether heparin priming of FNB needle improves tissue quality as compared to standard FNB for EUS-tissue acquisition of pancreatic masses.*

Secondary objectives:

- *Determine whether heparin priming of FNB needle improves cellularity.*
- *Determine whether heparin priming of FNB needle reduces blood contamination.*
- *Determine whether heparin priming of FNB needle improves histologic yield.*
- *Determine whether increasing number of FNB passes affects tissue quality, block contamination, and histologic yield.*
- *Determine the incremental diagnostic yield with a second or third FNB pass as compared to a single FNB pass.*

Hypothesis:

We hypothesize that the tissue quality of EUS-FNB specimens of pancreatic masses decreases with increasing pass number due to blood contamination. This blood contamination can be ameliorated with priming of the needle with an anticoagulant such as heparin, resulting in improved tissue quality of EUS-FNB of pancreatic masses.

Anticipated Results

- *We anticipate that histologic yield will decrease and blood contamination will increase with increasing number of FNB passes*
- *We anticipate that the intervention of heparin priming of the biopsy needle will decrease blood contamination and increase histologic yield.*

Trial design

- Single center, double-blind, superiority, parallel-group, 1:1 ratio, randomized controlled trial

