6 STUDY DESIGN AND PROCEDURES

Study setting: University of Michigan- Medical Procedure Unit

Study type: Clinical Trial

Assignment of Interventions:

Enrollment: 98 patients

Randomization: Subjects will be randomized in a 1:1 allocation ratio to the heparin group or the non-heparin control group at the time of intra-procedural decision to sample the mass. We will use restrictive block randomization to ensure balanced number of participants per group. The randomization sequence will be generated centrally from a computerized binary number generator at the University of Michigan. The treatment assignments will be in opaque sealed envelopes for allocation concealment. The study coordinator will enroll participants and will assign participants to the intervention. The randomization key will be kept under lock by the study coordinator until completion of the study period.

Blinding: The participants and the pathologist will be blinded to the group allocation. The proceduralist will not be blinded to allocation given the design of the study and for patient safety.

Interventions: all subjects will undergo EUS-FNB using linear echoendoscopes (GF-UCT180 Olympus America, Center Valley, Pa, USA). All EUS-FNB procedures will be performed by 1 of 5 experienced endosonographers ([name]). Once the site is identified, the lesion will be punctured using a 22-gauge Fork-tip needle (Sharkcore needle). The sampling technique will be at the discretion of the endoscopist (e.g. stylet vs. not stylet, suction vs. not suction, fanning technique vs. to-and-fro technique, number of strokes). A total of 3 FNB passes will be performed on every procedure. The use of rapid on-site cytopathology (ROSE) will be used at the discretion of the endoscopist and will not be mandatory for this study. The tissue specimens from each the 3 passes will be collected in 3 separate jars of 10% formalin for tissue analysis. The use of heparin flushing vs. not heparin flushing, will be based on their randomized group assignments:

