- Intervention group: The FNB needle will be flushed with 1 mL of heparin (100 USP/mL) and then flushed with air. Pass 1, 2, and 3 will be collected in separate jars and sent to pathology, as per standard clinical procedures. The study will pay for the cost of utilizing and submitting extra jars to pathology so that no extra cost is incurred to the patient for participating in the study. Between passes, after tissue is extracted from the needle, the needle will be flushed with 1 mL of heparin (100 USP/mL) and flushed with air before next pass is made.
- Control group: FNB will be performed as current standard methods in the medical procedure unit without the use of heparin priming. Pass 1, 2, and 3 will be collected in separate jars and sent to pathology, as per standard clinical procedures. The study will pay for the cost of utilizing and submitting extra jars to pathology so that no extra cost is incurred to the patient for participating in the study. Between passes, after tissue is extracted from the needle, the needle will be flushed saline and or air as per current standards of care.

If proceduralist feels that it is unsafe to continue with the research protocol during the procedure (examples would include inadequate tissue acquisition in the clinical jar, or clinical instability of patient during procedure), he or she reserves the right to withdraw the patient from the protocol. For patient safety, the proceduralist will not be blinded to whether the patient was randomized to the heparin or non-heparin arm. If the proceduralist deems more than 3 passes are needed for clinical purposes, the extra passes will go into a fourth jar.

Tissue Analysis:

H&E slides from the passes 1, 2, and 3 (which will be requested from pathology) will be compared in the following manner:

- A blinded clinical pathologist will examine each slide and determine
 - Is a tissue diagnosis able to be made?
 - Is the tissue adequate quality? The pathologist will create a reference scoring system and rate specimens accordingly.
- In parallel, using the HALO® image analysis platform (Indica Labs), each slide will be digitally scanned. The number of cells present on each H&E slide (cell-based analysis), the amount of blood present on each H&E slide (area-based analysis), and the size of each biopsy will be quantified (area-based analysis).

Tracking and labelling system

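### Sampling technique is left to an unblinded endoscopist, with no requirement to settle it before the arm is revealed, so technique could differ by arm and be mistaken for a heparin effect

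*Combined protocol and SAP*

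**What the plan says.** Section 6 (Study Design and Procedures) fixes the order of events. Randomization takes place "at the time of intra-procedural decision to sample the mass", and assignments are held in opaque sealed envelopes. On blinding it says "The participants and the pathologist will be blinded to the group allocation", and then "The proceduralist will not be blinded to allocation given the design of the study and for patient safety". The description of the two arms repeats that "the proceduralist will not be blinded to whether the patient was randomized to the heparin or non-heparin arm".

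On how tissue is taken, the Interventions paragraph says "The sampling technique will be at the discretion of the endoscopist" and gives as examples "stylet vs. not stylet, suction vs. not suction, fanning technique vs. to-and-fro technique, number of strokes". On-site cytopathology (ROSE) is also discretionary. In the heparin arm the needle is primed before the first pass, and between passes "the needle will be flushed with 1 mL of heparin (100 USP/mL) and flushed with air before next pass is made".

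Section 2 (Objectives) labels the design as "Single center, double-blind, superiority, parallel-group, 1:1 ratio, randomized controlled trial".

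Section 8 (Data Analysis) compares blood area, tissue area and cell number between arms, pass by pass, with Student t tests, and tissue score with chi-squared tests. No covariates are named. Section 6 describes blocked randomization and mentions no stratification by endoscopist. The data items in Section 7 do not include technique or operator.

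**The concern.** The outcomes are properties of the specimen: how many cells, how much blood, how much tissue, what score. Suction, needle movement and number of strokes help determine that specimen. The person who sets them knows the arm while doing so.

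Randomization balances what is fixed before allocation. It does not balance choices made after the arm is known. An operator who expects heparin to keep the needle clear might use more suction or more strokes in that arm. One who wants to compensate in the control arm might do the reverse. Either would shift the arm difference for a reason other than heparin. The blinded pathologist and the digital image analysis would then measure that shifted specimen accurately: they protect assessment, not acquisition.

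What is at stake is attribution. The primary objective in Section 2 asks whether heparin priming itself improves tissue quality. If technique differs by arm, neither a positive nor a null result answers that cleanly. Statistical adjustment cannot readily repair it, because technique chosen after allocation may itself be a consequence of the arm.

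**Working it through.** **1. The plan's own figure.** Inputs from the end of Section 8: SD 5 mm², difference 3 mm², power 80%, type I error 0.05, 10% dropout.

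n per arm = 2 × (1.960 + 0.842)² × 5² / 3² = 43.6, rounded up to 44. Total 88; 88 / 0.9 = 97.8, rounded up to 98. Both stated figures reproduce with a two-sided test. The normal-approximation power at 44 per arm is 80.4%.

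**2. Standard error of the arm difference.** SE = 5 × √(2/44) = 1.066 mm².

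**3. Bias from technique.** Bias = (mean effect of a technique choice on tissue area) × (difference between arms in how often it is used). The documents give neither quantity, so both are assumptions here: effects of 1 to 3 mm² and differences in use of 10 to 40 percentage points.

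**4. Consequences.** With no heparin effect, the two-sided rejection rate is 1 − Φ(1.96 − bias/SE) + Φ(−1.96 − bias/SE). If the bias opposes heparin, power for a true 3 mm² is the same expression with 3 − bias in place of bias.

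| Assumed technique effect | Difference in use | Bias (mm²) | Bias / SE | False-positive rate | Power for 3 mm² if bias opposes heparin |
|---|---|---|---|---|---|
| none | none | 0 | 0 | 5.0% | 80.4% |
| 1 mm² | 10 points | 0.1 | 0.09 | 5.1% | 77.7% |
| 2 mm² | 20 points | 0.4 | 0.38 | 6.6% | 68.4% |
| 3 mm² | 20 points | 0.6 | 0.56 | 8.7% | 61.5% |
| 3 mm² | 30 points | 0.9 | 0.84 | 13.5% | 50.4% |
| 3 mm² | 40 points | 1.2 | 1.13 | 20.3% | 39.3% |

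The top row is the nominal position. The 1 mm², 10-point case barely moves the false-positive rate. The bottom row assumes that one technique choice is worth the trial's whole target effect, together with a large imbalance in its use.

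**5. Scope.** The calculation uses tissue area because that is the only outcome with an SD in the documents. Section 8 lists cellularity and blood contamination as the primary outcomes. The same mechanism applies to them, but its size cannot be worked out from the documents.

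**The case against.** Free technique is a reasonable pragmatic choice. Section 1 criticizes the earlier crossover trial for relying on a single endoscopist, and five operators working in their own way answers that. On a pragmatic reading, a technique change prompted by allocation is part of the effect of assignment. This stands as a defense of discretion, and the proposal below keeps discretion. It does not fully meet the concern, because the stated objective is the effect of heparin priming.

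Unblinding is openly declared, and the heparin flush is part of the operator's own procedure. That also stands. The label in Section 2 is a matter of clear wording, not of concealment.

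Three stronger readings are tempting but not supported:

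- A reader might infer from Section 7 that technique goes unrecorded. That list is introduced as medical-record data. It also omits treatment arm, cell count and tissue score, which the trial must hold somewhere, and the schedule of events is not legible in the text available. The documents do not describe recording technique; they do not show that it is left out.
- A reader might infer that technique is always chosen after the arm is known. The documents do not say when it is chosen. An operator may already have settled on suction or stylet use by the time sampling is decided. The inference is firmer for strokes, which are carried out during the pass.
- A reader might take a false-positive rate of 9% or 20% as the expected error. Those figures need an assumed 3 mm² technique effect and a marked imbalance. Smaller values give almost nothing, and the bias could equally run against heparin.

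**Conclusion.** The concern holds as a risk to attribution. It is not a demonstrated bias. Section 6 itself supplies three elements: allocation at the decision to sample, an operator who knows the arm, and free choice of factors that shape the specimen. Nothing in the plan requires technique to be settled before the arm is revealed.

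Neither direction nor size can be determined from the documents. Over the assumed range of 1 to 3 mm² and 10 to 40 points, the false-positive rate for tissue area at 44 per arm lies between about 5% and about 20%. A 0.6 mm² bias against heparin takes power for a true 3 mm² from about 80% to about 61.5%. The planned sample size is not affected. The case for acting is that the safeguard is cheap, and that technique not noted at the time of each pass may be impossible to recover later.

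**What to change.** Add to Section 6:

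- Before the envelope is opened, the endoscopist records the intended suction, stylet use, movement technique, planned number of strokes and ROSE use, and follows that plan in either arm unless there is a clinical reason to depart.
- For each pass, the operator, the technique actually used and the reason for any departure are recorded.

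Add to Section 8: declared technique, actual technique and departures are reported by arm. Adjustment for declared technique or operator may be added for precision only. Declared technique is balanced by randomization in expectation, so adjusting for it cannot remove bias from departures made after allocation, and should not be presented as doing so.

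In Section 2, replace the bare double-blind label with a statement that participants and pathologist are blinded and the operator is not.

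The cost is a short checklist per procedure. Operator discretion, clinical care and the sample size are unchanged. Because departures remain allowed, the change limits arm-driven choices and makes any that remain visible. It does not eliminate them.

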3 EXPECTED RISKS/BENEFITS

There are no immediate benefits to participating in this study. Of note, IF a diagnosis of malignancy is made on the tissue obtained for research by a blinded clinical pathologist AND the diagnosis was not made on the passes obtained for clinical purposes, the patient will be notified. In this event, either the PI or one of the co-investigators (all of which are practicing physicians) will reach out to the patient personally to inform them of the discrepancy and make arrangements for the research block to be submitted to pathology for further evaluation. Furthermore, the patient's physician will be notified, and the patient will be referred to the appropriate medical specialist to treat the incidentally found condition.

The known or expected risks are:

- 1) Bleeding - EUS fine needle aspiration and EUS FNB rarely (<0.01%) cause bleeding but this is not expected to be increased measurably by the one additional pass made for research purposes. The risk of bleeding will be minimized by the use of experienced gastroenterologists who will perform the EUS FNBs with Doppler assistance to identify and avoid intervening vasculature during needle puncture.
- 2) Pancreatitis - A risk of EUS-FNB is pancreatitis, which is inflammation of the pancreas that is uncommonly severe. The reported risk ranges from 0-2% in the literature. It is unknown whether increased numbers of FNB passes increases the risk of pancreatitis. The risk of pancreatitis as a complication will be minimized by the use of experienced gastroenterologists who will perform the EUS procedures.
- 3) Infection - EUS fine needle aspiration and EUS FNB rarely (<0.01%) cause infection cases but this is not expected to be increased by the one additional pass made for research purposes.
- 4) Prolongation of procedure time - Acquisition of additional specimens during EUS will extend procedure duration by no more than 5 to 10 minutes. The only risk associated with this would be additional discomfort. This risk will be minimized through the continued use of sedative and pain medications given during the procedure. As per the standard of care, vital signs including oxygen saturation, heart rate, blood pressure, and cardiac rhythm will be continuously monitored.

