- 5) Confidentiality breach - Data produced and collected might be revealed to persons outside the study. This risk will be minimized through the use of a code number for the patient's name. The samples will be shared with other institutions and companies to conduct the research tests, but no information that identifies the patient will be shared.

Of note, we do not anticipate any extra risks from heparin priming of the needle, as the amount of heparin present in the needle would be a trace amount.

To further minimize research-related risk, only patient undergoing endoscopic FNB for clinical purposes will be consented for the research study.

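### The plan has no analysis rule for randomised patients whom an operator who knows the arm withdraws mid-procedure, so the separate per-pass tests can be biased at passes after withdrawal

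*Combined protocol and SAP*

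**What the plan says.** Section 6 (Study Design and Procedures) randomises at the point during the procedure when the operator decides to sample, so allocation comes before pass 1. On blinding it states: "The proceduralist will not be blinded to allocation given the design of the study and for patient safety". It then adds "If proceduralist feels that it is unsafe to continue with the research protocol during the procedure", and in that event "he or she reserves the right to withdraw the patient from the protocol". Two examples of a reason follow. One is clinical instability; for the other the text reads "examples would include inadequate tissue acquisition in the clinical jar". No threshold for inadequacy is set, and nothing is said about what happens to sampling or slides after withdrawal.

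Three passes are planned for everyone. For each arm the section says: "Pass 1, 2, and 3 will be collected in separate jars and sent to pathology, as per standard clinical procedures". For additional tissue it provides: "If the proceduralist deems more than 3 passes are needed for clinical purposes, the extra passes will go into a fourth jar". Section 3 (Expected Risks/Benefits) says that "only patient undergoing endoscopic FNB for clinical purposes will be consented for the research study", but its risk list speaks of "one additional pass made for research purposes".

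Section 8 (Data Analysis) lists Student t tests for blood area, tissue area and cell number, and chi-squared tests for the pathologist's tissue score. Each is run between arms separately at passes 1, 2 and 3, and between passes within each arm. It names no analysis set and no handling of missing passes. The 10% dropout allowance only raises the number recruited. Section 10 (Statistical Considerations) refers back to section 8 for the tests.

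**The concern.** The decision to withdraw comes after randomisation, is made by someone who knows the arm, and may rest on tissue yield, which is close to what the trial measures. If withdrawn patients contribute nothing to later passes, the patients compared at pass 2 or 3 are no longer the randomised groups. Suppose heparin improves yield and operators apply one standard to both arms. More controls are then withdrawn, the remaining controls are the better ones, and heparin looks less effective than it is. If operators instead withdraw heparin patients more readily, the error runs the other way. The blinded pathologist protects the scoring of slides, not the question of which slides exist or are counted. With no rule written down, who is analysed would be decided after the data are in hand.

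**Working it through.** **Inputs from section 8.** SD 5 mm² for tissue area, difference 3 mm² in total tissue area, power 80%, type I error 0.05, 10% dropout, 98 recruited (98/2 = 49 per arm).

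**The plan's own figure.** n per arm = 2 × (1.960 + 0.842)² × 5²/3² = 43.6, so 44. Then 88/0.9 = 97.8, so 98. Both reproduce, two-sided. With 49 per arm and no loss, t-test power is 83.6%.

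**Assumptions not in the documents.** The SD of 5 and the effect of 3 apply to a single pass. Correlation between passes is 0.5. The trigger is tissue area at the pass just taken. Passes after withdrawal are missing or excluded.

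**One cut-off for both arms.** Let the cut-off stop 10% of controls (z = −1.28), and let e be heparin's effect at the pass that prompts withdrawal, so z_h = z − e/5. The amount by which pass 3 understates heparin is

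0.5 × 5 × [φ(z)/0.90 − φ(z_h)/(1 − Φ(z_h))].

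At e = 3: 2.5 × (0.195 − 0.070) = 0.31 mm².

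| e (mm²) | Heparin patients stopped | Bias (mm²) | Simulated power |
|---|---|---|---|
| 0 | 10.0% | 0 | 82% |
| 0.5 | 8.4% | 0.07 | 81% |
| 1 | 6.9% | 0.13 | 80% |
| 2 | 4.6% | 0.23 | 77% |
| 3 | 3.0% | 0.31 | 74% |

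Simulation runs at e = 3 scatter around these values: about 0.30 to 0.33 mm², with power 73% to 75%.

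**Withdrawal after pass 2.** The protocol allows withdrawal at any time in the procedure. If heparin's effects are 0, 3 and 3 mm² at passes 1, 2 and 3, and the cut-off is applied after pass 2, then e is the pass 2 effect of 3. About 10% of controls and 3% of heparin patients are lost, and the pass 3 bias is again about 0.3 mm² with power about 74%.

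**Sensitivity, withdrawal after pass 1.**
- Between-pass correlation 0.3 to 0.7: 0.08 to 0.18 mm² at e = 1, and 0.19 to 0.44 mm² at e = 3.
- A trigger correlated only 0.5 with pass 1 area: at most 0.09 mm².
- Cut-off stopping 5% or 20% of controls, e = 3: 0.19 or 0.49 mm².

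**Unequal loss, no true effect.** Removing the 5 lowest of 49 controls and no heparin patients gives 0.193 × 0.5 × 5 = 0.48 mm² and type I error of about 8%. Losing 6 controls and 4 heparin patients gives 0.066 × 2.5 = 0.165 mm² and about 6%. At 15% control and 5% heparin loss the shift is 2.5 × (0.274 − 0.109) = 0.41 mm² against heparin. Swapping the percentages gives the same amount in its favour.

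**Cell number and blood area.** The plan gives no SDs. In SD units, the 5-to-0 loss gives 0.193 × r, where r is the correlation between trigger and pass 3 outcome: 0.02 at r = 0.1, 0.05 at 0.25 and 0.10 at 0.5.

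**Within-arm pass comparisons.** These shift even if both arms lose 10%. Controls left at pass 3 average 2.5 × 0.195 = 0.49 mm² above all controls.

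**Mixed model over all passes.** With true effect 3 and withdrawal after pass 1, separate t tests average about 2.85 (e = 1) and 2.64 to 2.68 (e = 3). A random-intercept model averages 2.98 to 3.00 and 2.95 to 2.99.

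**The case against.** The strongest reply is that slides may not be lost at all. Every patient is there for clinical sampling, three passes are planned, all go to pathology, and the stated response to needing more tissue is extra passes in a fourth jar. Poor tissue is then a reason to go on sampling. This stands in part: no section says that slides after withdrawal are missing or excluded. If they are taken with the same flush and included, simulation gives 2.99 mm² and 84% power, and nothing is wrong. But no section says that they are kept either, and the fourth jar covers passes beyond the third, not the analysis of a withdrawn patient.

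A second reply is that the bias is small. That is true in most of the cases above; the larger ones need one-sided loss or a large heparin effect at the pass that prompts withdrawal. A third is that this is a pilot. It is also described as a superiority trial and powered at 80%.

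The trigger wording may itself be left over from another design, because a single clinical jar does not fit three jars that all go to pathology. That is a reason to clarify it, not to ignore it.

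Two stronger inferences fail. A reader might conclude that heparin's effect will be understated. The documents give no withdrawal rate and no sign of which arm would lose more, so neither the presence nor the direction of bias is established. A reader might also conclude that there is no bias if heparin acts only from pass 2. That holds only if withdrawal can occur solely after pass 1, and section 6 does not limit it so.

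**Conclusion.** The point holds as a conditional one. The plan permits outcome-related withdrawal after randomisation by an operator who knows the arm, and its per-pass tests carry no rule for the result. Bias at later passes arises only if their slides are missing or excluded and the arms differ in how many patients, or which patients, are lost. The true size cannot be known from the documents; the range of 0 to about 0.3 mm² against a 3 mm² effect rests on the assumed cut-off, correlation and single-pass effect set out above. This is a matter the sponsor should settle before analysis. It does not show that the trial's result will be wrong, and it is no criticism of the operator's freedom to withdraw a patient.

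**What to change.** Leave the operator's decision as it is and change the analysis text:

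1. Analyse all randomised patients in their assigned arm. Include every available, separately identifiable slide from passes 1 to 3, including the pass that prompted withdrawal, and flag any pass taken off protocol.
2. For cell number, blood area and tissue area, replace the separate t tests, both between arms and between passes within arm, with one mixed model: arm, pass, arm by pass, and a patient random effect.
3. Record and report withdrawals by arm, pass and reason.
4. For the pathologist's tissue score, add a sensitivity analysis that counts a pass as not adequate only when it is missing because of inadequate tissue. Passes missing through clinical instability should not be scored this way.
5. Reconcile the single clinical jar in section 6 and the single extra research pass in section 3 with the three-jar design, and state whether passes taken after withdrawal count as study passes.

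The cost is protocol and SAP wording, one line on the procedure form and slightly more analysis work, with no extra patients or procedures. There are two limits. If withdrawal depends on an unrecorded impression of the patient, the model corrects only part of the bias (0.31 down to 0.15 mm² with 5 controls and no heparin patients lost). If withdrawn heparin patients later have passes without heparin, keeping them in their arm dilutes the estimate: with 3.4 of 49 affected, 3 × (1 − 3.4/49) is about 2.8 mm², with power about 75%. The off-protocol flag allows this to be shown.

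### Section 6 lets an unblinded operator withdraw randomized patients for poor tissue in a clinical jar that the three-jar design does not define, and does not say how this relates to the fourth-jar rule

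*Combined protocol and SAP*

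**What the plan says.** All of the following is in Section 6 of the combined protocol and SAP, except where noted.

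- **Jars.** "The tissue specimens from each the 3 passes will be collected in 3 separate jars of 10% formalin for tissue analysis". Both arm descriptions add: "Pass 1, 2, and 3 will be collected in separate jars and sent to pathology, as per standard clinical procedures". Every jar is therefore both a clinical specimen and a study specimen.
- **Withdrawal.** The condition is "If proceduralist feels that it is unsafe to continue with the research protocol during the procedure", the illustration is "examples would include inadequate tissue acquisition in the clinical jar, or clinical instability of patient during procedure", and the consequence is that "he or she reserves the right to withdraw the patient from the protocol".
- **Extra passes.** "If the proceduralist deems more than 3 passes are needed for clinical purposes, the extra passes will go into a fourth jar". Nothing is said about that patient's study status.
- **Blinding.** In the same paragraph, "the proceduralist will not be blinded to whether the patient was randomized to the heparin or non-heparin arm".
- **Timing.** Randomization takes place when the decision to sample the mass is made during the procedure, so before the first pass.
- **Section 3.** The bleeding paragraph states that "this is not expected to be increased measurably by the one additional pass made for research purposes". The section separates passes taken for clinical purposes from tissue taken for research, a split that the three-jar design does not have.

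**The concern.** The withdrawal example turns on a jar that cannot be identified. It could mean the first jar, any of the three, or all three together, and no criterion for inadequate tissue is given. On-site cytopathology is optional, so the judgement may rest on the operator's impression alone.

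Once three passes have been taken and the tissue still looks poor, the withdrawal sentence and the fourth-jar sentence can both be invoked, with no stated order between them. Two operators facing the same patient could follow the protocol and act differently.

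Three features make this more than loose wording. The decision comes after randomization. It is made by someone who knows the arm. It depends on an impression of tissue yield, which is related to the outcomes and to tissue area, the variable on which the trial is sized. If patients with poor yield drop out of the analysis, and the treatment changes how many there are, the remaining groups are no longer comparable. The data items listed in Section 7 include no reason for withdrawal, no pass number at withdrawal and no count of extra passes, so selective loss would be hard to see afterwards.

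**Working it through.** **Reading the two rules together**

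| Situation | Withdrawal sentence | Fourth-jar sentence |
|---|---|---|
| Tissue looks poor after pass 1 or 2 | May apply, if continuing is felt to be unsafe | Does not apply; three passes are not yet done |
| Tissue looks poor after pass 3 | May apply | May apply |
| Patient clinically unstable | May apply | Not relevant |

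The triggers overlap in the second row only. The undefined jar affects the first two rows.

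**The plan's own sample size** (Section 8: difference 3 mm², SD 5 mm², power 80%, type I error 0.05, dropout 10%; sidedness is not stated, and two-sided reproduces the figure)

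n per arm = 2 × (1.960 + 0.842)² × 5² / 3² = 43.6, so 44. Recruitment = 88 / 0.9 = 97.8, so 98, or 49 per arm. Both figures match the plan. With all 49 per arm analysed, power by the t-test is about 84%.

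**Illustration: one cut-off, applied identically in both arms**

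Assumptions, none from the documents: tissue area is normal in each arm; patients below the cut-off are withdrawn and excluded from the analysis; the operator's impression agrees perfectly with measured area. The cut-off is set to remove the lowest 10% of controls. The SD of 5 mm² and the true difference of 3 mm² are the plan's.

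1. Standardized cut-off in controls: z = −1.282.
2. The same cut-off in the heparin arm: −1.282 − 3/5 = −1.882, which removes 3.0%.
3. Rise in an arm's mean after truncation = SD × φ(z) / (1 − proportion removed).
   - Controls: 5 × 0.1755 / 0.90 = 0.97 mm².
   - Heparin: 5 × 0.0679 / 0.970 = 0.35 mm².
4. Remaining difference: 3 + 0.35 − 0.97 = 2.38 mm², about 2.4 mm².

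Simulation with 49 per arm (10,000 runs) gave the same difference and a power of about 72%. A cut-off removing the lowest 20% of controls removes 7.5% of heparin patients; the difference falls to about 2.0 mm² and power to about 60%.

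In the first case the loss is 0.10 × 49 + 0.03 × 49 = 6.4 patients of 98, or 6.5%. That is inside the plan's 10% dropout allowance, so the allowance does not protect against this bias.

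**If use of the rule differs by arm**

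With no true effect, and the lowest 10% of the heparin arm alone withdrawn and excluded, two-sided rejection rises from 5% to about 16% in simulation. If instead each arm loses the lowest 10% of its own patients, the difference stays at 3.0 mm² and the type I error at about 5%. The harm comes from unequal loss, not from loss as such.

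**The case against.** The strongest reply is that the two sentences can be read in sequence: a safety exit while the study passes are under way, then a destination for clinical passes once they are complete. Poor tissue is only an example of when continuing might be unsafe, and withdrawal is a right, not a duty. This largely stands. A reader might infer that Section 6 orders two opposite outcomes for one event; the documents do not support that, because the triggers are worded differently and coincide only after pass 3. A reader might also infer that a fourth-jar patient is kept in the study. The separate jar suggests it, but the text states only where the extra tissue goes.

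A second reply concerns size. A reader might take per-pass inadequacy of, say, 10–20%, count every patient with any poor jar (1 − 0.9³ = 27% to 1 − 0.8³ = 49%, with independent passes), and conclude that power collapses. That goes too far. By the time jar 3 is judged, no study pass remains to be stopped. Counting jars 1 and 2 only gives 1 − 0.9² = 19% to 1 − 0.8² = 36%. That leaves 49 × 0.81 = 39.7 to 49 × 0.64 = 31.4 per arm and a power of about 75% to 65%. Even this is an upper bound under the assumed rates, since it treats every poor jar as a withdrawal and every withdrawn patient as wholly lost. Section 8 compares the arms pass by pass, so passes already taken could still be used.

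Third, the trigger is an impression during the procedure, whereas the outcomes come from image analysis and a blinded pathologist. The primary outcomes listed in Section 8 are cellularity and blood contamination, not tissue area. This also stands: the link is one of correlation, and the illustration, which assumes perfect agreement, overstates the effect to an unknown degree.

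What none of these replies answers is that the jar has no referent, that the order of the two rules is unstated, and that the plan does not say what happens to passes already obtained.

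**Conclusion.** The point holds as an undefined trigger combined with two overlapping discretionary rules. The wording fits the clinical and research split that survives in Section 3 rather than the three-jar procedure in Section 6. Followed as written, it permits loss after randomization that depends on apparent tissue yield and is decided with knowledge of the arm.

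The size cannot be predicted, because the documents give no inadequacy or withdrawal rate. Under the assumptions listed in the working, a cut-off applied evenly to both arms reduces a true 3 mm² difference to about 2.4 mm² (10% of controls removed) or 2.0 mm² (20% removed). The bias arises only if withdrawn patients are lost from the analysis, which the plan neither states nor rules out. It is worth correcting before enrolment proceeds, since the correction is small and the effect could not be diagnosed later from the data items now listed.

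**What to change.** - Reconcile the withdrawal and fourth-jar sentences in Section 6, together with the matching clinical and research wording in Section 3, so that the relation between the two rules is stated. Which clinical rule applies is for the investigators.
- Replace the reference to the clinical jar with a term that exists in the three-jar design.
- State the study status of a patient who has extra passes. State also that study passes already obtained from any withdrawn or fourth-jar patient are retained and analysed in the arm to which the patient was randomized.
- Record, by arm, the reason for and the pass number at each withdrawal or extra pass.

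The cost is a few sentences of amendment and one or two data fields, with no extra patients or procedures. The downside is that some low-yield specimens that might have been dropped will enter the analysis. Passes never taken from withdrawn patients will still be missing, but the record will show how many and in which arm.
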